3.1. PARTICIPANT ORGANIZATION

3.1.1. Study Centers

Each clinical center consists of an interdisciplinary team of investigators who provide the areas of expertise necessary for the successful completion of the SEARCH protocol. Clinical center responsibilities include:

- a) Collaborating in design and monitoring of the study, including regular attendance at Steering Committee meetings and participation in study-wide committees;
- b) Identifying children and youth eligible for the study;
- c) Recruiting and retaining study participants;
- d) Collecting high quality data in a systematic and standardized fashion consistent with the study protocol; and,
- e) Collaborating in the analysis and dissemination of study results.
- 3.1.2. Coordinating Center

The Coordinating Center (CoC) has primary responsibility for monitoring quality and analyzing data generated in the study. Additional responsibilities of the Coordinating Center include:

- a) Preparing the protocol, forms, manuals, and educational and recruitment materials with the guidance and assistance of study investigators, Centers for Disease Control and Prevention (CDC), and National Institutes of Health (NIH) personnel;
- b) Collaborating on development of the statistical design;
- c) Working with the investigators in developing and pre-testing data collection forms and procedures, and assuming responsibility for the translation, reproduction and distribution of forms, hardware, and software associated with data entry;
- d) Training data coordinators and other clinical center research support personnel;
- e) Assuring data quality, study performance, and laboratory procedures;
- f) Summarizing clinical center performance at regular intervals for the Study group;
- g) Providing detailed reports regarding eligible participants, participant recruitment and data collection;
- h) Providing support for committee meetings and conference calls; and,

i) Preparing, in collaboration with the clinical investigators, various manuscripts of study results.

3.1.3. Central Laboratory

The central laboratory has primary responsibility for training clinical center personnel on blood draw, processing and shipping procedures, monitoring quality of samples received, ensuring that samples are tested according to study protocol, and generating laboratory results for the study. Additional responsibilities of the Central Laboratory include:

- a) Developing and distributing a laboratory manual of procedures;
- b) Participating in Protocol Oversight and Steering Committee meetings and conference calls;
- c) Providing supplies and support to clinical centers as needed;
- d) Preparing monthly quality control reports for clinical centers;
- e) Transmitting laboratory data to the CoC; and,
- f) Participating as a scientific collaborator with SEARCH investigators.
- 3.1.4. Federal Sponsors

SEARCH is sponsored by the CDC Division of Diabetes Translation (DDT) and supported by the National Institute of Diabetes and Digestive and Kidney Diseases (NIDDK) of the National Institutes of Health. The SEARCH study centers are funded by a cooperative agreement, and the Coordinating Center is funded through a contract. The CDC Project Office is responsible for the funding, cooperative agreement administration, monitoring, and overall scientific integrity of the study. While the Principal Investigators will lead the scientific aspects of the study, representatives of the Federal agencies (CDC/NIDDK) will participate in all phases of planning, scientific design, implementation, evaluation and communicating results relating to SEARCH.

The CDC reserves the right to prematurely terminate or curtail the study (or an individual award) in the event of human subject ethical issues that cannot be resolved.

3.1.5. External Scientific Evaluation Committee (ESEC)

The External Scientific Evaluation Committee (ESEC) includes experts in the fields of diabetes, pediatrics, epidemiology, biostatistics, and health services research, augmented with ad hoc members as necessary, with appointments being made by the CDC in consultation with other sponsors. Members are completely independent of the SEARCH study centers and affiliated investigators. The ESEC reviews progress and conduct of the research. ESEC will advise the sponsors of any concerns and/or make recommendations regarding continuation, termination, or modification of studies. ESEC meets annually and hold additional meetings or conference calls as required for adequate monitoring.

3.1.6. Data Ownership

The data collected as part of SEARCH will belong to the respective clinical centers, and not the government or the Coordinating Center. The Principal Investigator of each center will be the responsible custodian of the data. All personally identifiable data will reside at the respective clinical centers and will not be transmitted to the Coordinating Center. Data collected by the University of Colorado Denver on Navajo Nation participants belong to the Navajo Nation, as stipulated in the Memorandum of Understanding. As part of the SEARCH cooperative agreement and collaboration, each clinical center will share non- personally identifiable data with the coordinating center to create aggregate data sets, perform analysis, and prepare scientific presentations and communications. Additionally at the conclusion of the SEARCH study, a de-identified data set is required to be provided to the CDC and archived in a repository.

3.2. COMMITTEE STRUCTURE

3.2.1. Study-wide Committees

The following study-wide committees are established for SEARCH:

3.2.1.1. Study Group

The Study Group consists of everyone actively participating in the SEARCH study. Members of the Study Group who are not on the Steering Committee will participate in SEARCH through membership in standing committees, task groups, and writing groups and attendance at meetings when requested.

The Study Group will meet monthly by conference call. These calls will serve primarily to convey study status and as informational sessions. Members of the Study Group who are not members of the Steering Committee will attend in-person meetings as needed to conduct the work of SEARCH.

3.2.1.2. Steering Committee

The Steering Committee will accomplish the scientific work of SEARCH. The Steering Committee will consist of the PI and one other member from each clinical center, the chairs of main study-wide committees (see below), two members from the CDC, one member from the NIDDK, the Co-PIs from the CoC, and the PI from the Central Laboratory. The Steering Committee will meet via conference call and as needed during face-to-face meetings.

Clinical centers and the CoC will designate specific individuals as members of the Steering Committee. Only these individuals will participate in calls. Alternates can attend Steering Committee meetings when it is impossible for the designated members of this committee to attend.

All members of the Steering Committee are full participants in discussions and work of this committee. In matters that require a vote, each study center will have one vote, including Clinical Centers, Coordinating Center, Central Laboratory, CDC and NIDDK.

The Steering Committee makes final decisions on protocol changes, gives final approval prior to submission for all manuscripts, and directs the work of standing committees and Task Groups.

3.2.1.3. Executive Committee

The Executive Committee will consist of the study co-chairs, the CDC and NIDDK Project Officer, the CoC Co-PIs, and one of the P&P co-chairs. The chairs of the Ancillary Studies, Registry Oversight and Outcomes Committees will be asked to meet with the Executive Committee as needed. The committee will meet via conference call to set the agendas for the calls and meetings, set priorities for use of call and meeting time, and to troubleshoot administrative problems as needed.

3.2.1.4. Protocol Oversight Committee

The Protocol Oversight Committee (POC) will consist of representatives across the clinical centers, the CoC and the CDC. The POC will have co-chairs and voting members. Because of the nature of the committee's charge, the chair of POC will be the Director of the CoC. The committee will be responsible for reviewing aspects of the study protocol, including data quality control, adverse events, and recruitment and retention. The POC will also make recommendations to the Steering Committee on modifications to the study MOP and Protocol. The committee will report to the Study Group on a regular basis.

3.2.1.5. Publications and Presentations Committee

The Publications and Presentations (P & P) Committee will consist of representatives from clinical centers, the CoC, the CDC and the Central Laboratory; representing a range of scientific expertise relevant to major aims of SEARCH. The P & P committee will not necessarily include representatives from all centers. The P & P committee will consist of SEARCH investigators with expertise in surveillance, epidemiologic methods, biostatistics, complications, risk factors for complications, health services research. This P & P committee will have co-chairs and voting members; and one of the co-chairs will be a member of the Executive Committee. The committee will be responsible for reviewing and approving: abstracts; manuscripts; posters and oral presentations from SEARCH and its ancillary studies. The P & P committee is responsible for monitoring progress on manuscripts and presentations based on data from the main SEARCH study.

3.2.1.6. Ancillary Studies Committee

The Ancillary Studies Committee will consist of representatives from clinical centers, the CoC, the CDC and the Central Laboratory; representing a range of scientific expertise relevant to major aims of SEARCH. This committee will have co-chairs and voting members. The Ancillary Studies Committee will have the responsibility of approving ancillary study proposals from SEARCH and non-SEARCH investigators.

3.2.1.7. Registry Oversight Committee

The Registry Oversight Committee (ROC) will consist of up to 10 members, not necessarily from each clinical center, with expertise and interest in epidemiologic and surveillance methods, study logistics, and biostatistics. This committee will have co-chairs, and voting members. Nominations will be made to the study co-chairs and the executive committee will determine the final membership. The ROC will provide oversight of issues concerning denominator estimation, including by race/ethnicity, completeness of case ascertainment, periodic case re-ascertainment, trends in incidence rates and prevalence, mortality surveillance and other areas as assigned by the executive committee.

3.2.1.8. Outcomes Committee

The Outcomes Committee will consist of representatives from clinical centers, the CoC, the CDC and the Central Laboratory, representing a range of scientific expertise relevant to major aims of SEARCH. The Outcomes Committee will focus on reviewing results of outcome measurements (retinopathy, neuropathy, arterial stiffness, nephropathy), developing and monitoring protocols, organizing feedback to participants. The committee will have co-chairs and voting members, with particular emphasis on clinicians, project managers and investigators and staff with relevant expertise.

3.2.1.9. Recruitment and Retention Committee

The Recruitment and Retention (R & R) Committee will consist of representatives from clinical centers and the CoC. The R & R committee will have a chair who will serve one year terms. The Recruitment and Retention Committee will be responsible for developing strategies for enhancing the recruitment and retention of SEARCH participants. The committee will meet monthly via conference call, and will provide feedback to the Study Group on a regular basis.

3.2.1.10. Project Managers Committee

The Project Managers Committee will consist of representatives across clinical centers and the CoC. The Project Managers will have a chair and voting members.

The chair will serve one year terms. The committee will be responsible for providing input to the Protocol Oversight Committee regarding clinic operations, recruitment and retention, and various aspects of protocol oversight. The committee will report to the Study Group on a regular basis.

3.2.2. Face-to-Face Meetings

Face-to-face meetings of the Steering Committee will be held on a regular basis. The priorities for these meetings are determined by the Steering Committee.

Members of the Study Group who are not members of the Steering Committee are invited to the face-to-face meetings as needed to accomplish the work of SEARCH.

Other face-to-face meetings of writing groups, task groups or standing committees are held on an as-needed basis, usually in conjunction with Steering Committee meetings. Meetings independent of the Steering Committee meeting will require prior approval by the Steering Committee.

4.1. SEARCH REGISTRY STUDY OBJECTIVES

4.1.1. Goals

SEARCH for Diabetes in Youth originally began in 2000 as a multi-center, epidemiological study, conducted in six geographically dispersed Study Centers that encompassed the racial and ethnic diversity of the U.S. The study was designed to estimate the prevalence and incidence of diabetes among youth age < 20 years, according to diabetes type, age, sex, and race/ethnicity, and to characterize selected acute and chronic complications of diabetes and their risk factors, as well as the quality of life and quality of health care. Major strengths of SEARCH include 1) race/ethnic diversity within the large cohort of youth with type 1 diabetes (T1D); and 2) size and diversity of the cohort of youth with type 2 diabetes (T2D). In addition, SEARCH has substantially contributed to the understanding of the etiologic and clinical dimensions of childhood diabetes that relate to classification of diabetes. Critical questions remain regarding ongoing trends in incidence of childhood diabetes, as well as the rationale and sustainability of public health surveillance systems for diabetes in youth. SEARCH is exceptionally strongly positioned to address these questions through its well-established infrastructure and surveillance system, and its highly experienced, collaborative and multi-disciplinary investigative team.

The SEARCH for Diabetes in Youth Registry Study in SEARCH Phase 3 will continue to ascertain newly diagnosed incident diabetes cases in youth age < 20 years across five geographically dispersed Study Centers (Ohio, Colorado, Washington, South Carolina, and California) in order to accomplish the Specific Aims shown below.

Aim 1: To continue to ascertain newly diagnosed (2010 - 2014) incident diabetes cases in youth age < 20 years in order to assess temporal trends in diabetes incidence and temporal trends in presentation of diabetes for the period 2002-2014, by age, sex, race/ethnicity, and diabetes type.

Research Question 1.1: What is the temporal trend of Type 1 Diabetes (T1D) incidence in US youth and how does this differ by race/ethnicity, age, and gender?

Research Question 1.2: What is the temporal trend of Type 2 Diabetes (T2D) incidence in US youth and how does this differ by race/ethnicity, age, and gender?

Research Question 1.3: Are there temporal changes in the clinical characteristics at onset of diabetes in youth and how do these differ by a) clinical diabetes type (T1D versus T2D); b) race/ethnicity (non-Hispanic white versus minority); and c) sex (males versus females)?

Specific characteristics to be examined are: age at onset of diabetes, markers of disease severity (diabetic ketoacidosis, residual insulin secretion, HbA_{1c}), immunogenetic markers (diabetes autoantibodies, HLA risk genotypes), markers of insulin sensitivity (insulin sensitivity score, waist circumference, body mass index), cardio-vascular risk factors (lipid profile, blood pressure, microalbuminuria).

Aim 2: To provide consultation and support to inform the development of low-cost sustainable public health surveillance systems of childhood diabetes in the U.S., with a focus on challenges in ascertainment of cases with T2D and cases among older youth (ages 15 years or older) with any form of non-gestational diabetes.

Research Question 2.1: Within the SEARCH surveillance system, what factors contribute to time from diagnosis to case ascertainment? Can an extended period of time to case ascertainment be accounted for by the time to receipt of specialty care or hospitalization? Are there temporal changes in time to case ascertainment?

Research Question 2.2: Within and across health care systems, using the same case ascertainment algorithm, are patterns of care different for youth with T2D or older youth with any type of diabetes, around the time of clinical diagnosis, and thereafter? Are there temporal changes in observed differences, both within and across systems?

Aim 3: Assess total and cause-specific mortality among 2002-2008 incident cases for the period from the date of diabetes diagnosis through December 31, 2010.

Research Question 3.1: Are the frequency and causes of mortality in youth with diabetes different than non-diabetic, age comparable youth? Among youth with diabetes, does the frequency of mortality differ by type of diabetes, race/ethnicity or other socio-cultural factors?

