De-duplication: Duplicates will be identified using both electronic files and manually, both within and between case sources, using the name or initials, gender, date of birth, ethnicity, zip code, or other available information, in keeping with HIPAA requirements to use the least amount of PHI in conducting research. The number of duplicates identified will be used to estimate completeness of ascertainment with the capture-recapture method among the geographic centers.

Systematic re-ascertainment: A systematic case re-ascertainment process will be conducted in 2012 for cases incident in 2006-2010 and in 2014 for 2008-2012 cohorts. The purpose of re-ascertainment is to assure as complete ascertainment of diabetes cases as possible, especially those with T2D, who, due to different care patterns, we theorize are more likely to be missed by the SEARCH network prior to the close of the registration window. Additional cases will be registered with the center and the CoC with a flag to indicate that they were registered outside of the standard window.

Case Registration: Cases that are valid, eligible and unique will be registered by the center with information being uploaded to the CoC. Minimal information about the participant (age, gender, race/ethnicity, type of diabetes reported by clinician, center, date of diagnosis, zip code or county of residence, and birth date) will be uploaded to the CoC website in order to protect confidentiality. Names and addresses are not provided to the CoC. In cases where duplicates and cases that are not valid or eligible are identified at a later date, they will be unregistered by both the local center and the CoC.

Collection of Core Variables: A minimum amount of demographic and clinical information is needed for all registered cases in order for the study to be able to provide population-based rates of diabetes mellitus by age, gender, diabetes type and race/ethnicity for the entire population of cases. This information is also critical in assessing possible response bias to the in person research visit. This information is called "core" information. The main sources of core data are medical records and the initial participant survey and are described in Table 5 - 1.

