6.4. EVALUATING CASE ASCERTAINMENT STRATEGIES: ANALYSIS OF SEARCH REGISTRY DATA

For research question 2.1, we will evaluate (a) whether a longer period of calendar time is required to ascertain cases of youth with T2D or older youth with any type of diabetes than youth with T1D and younger youth; (b) whether any calendar time difference in ascertainment by diabetes type and age can be accounted for by the time from clinical diagnosis to hospitalization or receipt of specialty care services; and (c) if there are temporal changes in observed differences in time to case ascertainment. Date of diagnosis, date of birth, sex, clinical diabetes type, type of health care provider (pediatric endocrinologists, pediatricians, family practice physicians, adult endocrinologists) and the system in which each youth with diabetes received their care (community clinic, university based health system, managed health care organization) around the time of diagnosis are obtained from the medical record, the IPS, or administrative data sources at the time of case validation. Calendar time from date of diagnosis to date of case registration will be calculated in months so that time from diagnosis to registration can be compared by type within each category as well as within type by age category.

Using this information from SEARCH registered cases we will be able to quantify the timing and completeness of case ascertainment under a variety of scenarios. For example, we can simulate specific ascertainment scenarios to compare the completeness of ascertainment of youth with T1D versus T2D by age category if a system relied solely on pediatric endocrinology and hospital-based surveillance networks as compared to if a system that relied on these sources plus primary care providers. We will identify efficient ways to optimize ascertainment of youth with T1D or T2D, using data collected to date by the SEARCH study and through the 2011 incident cohort. This approach goes beyond examining variation by study centers and takes advantage of the diversity within and between the existing SEARCH study centers which conduct ascertainment state-wide (SC, CO), in defined regions (WA, OH), from enrollees in managed health care organizations (CA), and from enrollees in IHS facilities.

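### Section 6.4 compares diagnosis-to-registration delay among registered cases without allowing for right truncation or for re-ascertainment looks that differ by incident year

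*Protocol*

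**What the plan says.** Research Question 2.1 (Section 4A, 4.1.1) asks "Within the SEARCH surveillance system, what factors contribute to time from diagnosis to case ascertainment", whether a long time can be explained by the time to specialty care or hospitalization, and whether it changes over calendar time.

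Section 6.4 (Section 6A) fixes the outcome: "Calendar time from date of diagnosis to date of case registration will be calculated in months", for comparison by type and by age. The data set is also fixed: "Using this information from SEARCH registered cases we will be able to quantify the timing and completeness of case ascertainment", and the best ascertainment routes are to be found "using data collected to date by the SEARCH study and through the 2011 incident cohort". Truncation is not mentioned.

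Section 5.1.2 (Section 5A) gives the reason for re-ascertainment: T2D cases, it theorizes, "are more likely to be missed by the SEARCH network prior to the close of the registration window". It then gives the schedule: "A systematic case re-ascertainment process will be conducted in 2012 for cases incident in 2006-2010 and in 2014 for 2008-2012 cohorts". Cases found this way are registered with a "flag to indicate that they were registered outside of the standard window". The Executive Summary adds that earlier years will be re-ascertained periodically, without dates. No date is stated for the 2002-2005 cohorts. Neither section gives the length of the standard window or says whether flagged cases enter the delay comparison.

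**The concern.** A case that is never registered has no delay value. Delays among registered cases are therefore right-truncated at the last look, and the longest ones drop out. On the protocol's own theory, this removes more T2D than T1D cases, and T2D is the group Aim 2 is about.

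The last look also differs by incident year. The stated schedule gives 2006 and 2007 one sweep (2012), 2008 to 2010 two sweeps (2012 and 2014), 2011 one sweep (2014), and 2002-2005 none. A swept-in case carries a delay that reflects when the sweep was run rather than how the care system found the case.

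All three parts of the question are affected: the size of the T2D and older-youth delay, how much of it specialty care or hospitalization explains, and whether it has changed. These answers feed the surveillance advice that Aim 2 is to provide.

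**Working it through.** The protocol states no delay, power or bias figure for this question, so there is nothing to reproduce.

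**Inputs from the protocol.** Registered cases only; sweeps in 2012 for 2006-2010 and in 2014 for 2008-2012; late cases registered with a flag.

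**Assumed inputs, none of them in the protocol.** Diagnosis uniform over the index year; exponential delays with mean m = 3 months (T1D) and 9 or 12 months (T2D); window closing w = 6, 12 or 18 months after year-end.

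**Case 1: late cases left out.** A case diagnosed in month u is seen only if its delay is at most T = 12 + w − u. Averaging over u:

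- share missed: q = (m/12)[e^(−w/m) − e^(−(12+w)/m)]
- B = average of T·e^(−T/m) = (m/12)[(w+m)e^(−w/m) − (12+w+m)e^(−(12+w)/m)]
- observed mean = [m(1−q) − B]/(1−q)

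For w = 12:

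- T2D, m = 9: q = 0.75(0.2636 − 0.0695) = 0.1456; B = 0.75(21×0.2636 − 33×0.0695) = 2.432; mean = 5.258/0.8544 = 6.15.
- T1D, m = 3: q = 0.0045; B = 0.0664; mean = 2.920/0.9955 = 2.93.
- Observed gap 3.22 months against a true 6, so 46% is lost.

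| Window close after year-end | 3 vs 9 months (true gap 6) | 3 vs 12 months (true gap 9) |
|---|---|---|
| 6 months | 2.06 seen, 66% lost | 2.45 seen, 73% lost |
| 12 months | 3.22 seen, 46% lost | 3.91 seen, 57% lost |
| 18 months | 4.18 seen, 30% lost | 5.23 seen, 42% lost |

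Lognormal delays (sigma 1) with the same means lose 37% to 67%. Medians lose less: 29% and 40% in the 12-month row under exponential delays.

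**Case 2: flagged late cases included.** Further assumptions: means of 3 and 9 months, w = 12, mid-year sweeps, each catching half of the cases still missed, no true change over time. The mean diagnosis month of missed cases is 24 − B/q, which is 7.30 (T2D) and 9.22 (T1D).

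For the 2006 cohort, the mid-2012 sweep falls at month 78:

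- T2D: 0.0728 of cases are added with mean delay 78 − 7.30 = 70.7. Mean = (5.258 + 0.0728×70.7)/(0.8544 + 0.0728) = 11.22.
- T1D: 0.00225 are added with mean delay 68.8. Mean = (2.920 + 0.155)/0.9978 = 3.08.
- Gap 8.1 months against a true 6.

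The same formula for every year, with the second sweep taking half of the remainder for 2008-2010:

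| Incident year | 2005 | 2006 | 2007 | 2008 | 2009 | 2010 | 2011 |
|---|---|---|---|---|---|---|---|
| Apparent gap (true 6.0) | 3.2 | 8.1 | 7.2 | 8.6 | 7.2 | 5.9 | 5.4 |

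The pattern follows the sweep dates alone. If a sweep catches a quarter of missed cases, the range is 3.2 to 6.6; if it catches three quarters, 3.2 to 10.3.

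**The case against.** The strongest reply is that the plan does not discard late cases. A reader might infer that the comparison uses only cases registered before the window closes. The documents do not support that: Section 5.1.2 registers late cases with a flag, and Section 6.4 speaks of registered cases without excluding them. It follows that bias toward zero is not established for the plan as written. If flagged cases enter, a 2006 case found in the 2012 sweep has a delay of about six years, which can widen the gap. Both points stand. They do not rescue the comparison, because Case 2 shows it then follows the sweep calendar.

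A second reply is that longer looks shrink the loss. At assumed means of 3 and 12 months, a fixed cut-off loses 42% of the mean gap at 24 months after diagnosis, 10% at 48 and 2% at 72. That is correct for delays that run their natural course, but not for delays set by a sweep.

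A third is that the summary statistic and model belong in an analysis plan. Section 6.4 names no mean, median or test, so that much is fair. The outcome, the registered-case set and the sweep schedule are fixed here, however, and they create the problem whichever statistic is chosen.

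It is also tempting to say that registration is the wrong endpoint for a question about ascertainment. Section 5.1.1 counts registration as part of ascertainment, so that does not hold.

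**Conclusion.** The point holds in this form: the delay comparison in Section 6.4, read with Section 5.1.2, ignores right truncation and unequal looks, and does not say how flagged late cases are treated. Without those cases, the T2D-T1D gap is biased toward zero. With them, it can be over- or understated and can show a trend that is not there.

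The size cannot be fixed from the protocol. Under the assumed exponential means of 3 versus 9 to 12 months, 30% to 73% of the mean gap is lost for a cut-off 6 to 18 months after year-end. With sweeps that catch half of the missed cases, a constant 6-month gap appears as 3.2 to 8.6 months across incident years. A reader might take from the middle of the first range that about half the gap is lost; that is one point under assumed inputs, and other windows and means give anything from almost none to over 90%. The direction with late cases excluded rests on the protocol's own theory that T2D cases miss the window more often.

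**What to change.** In Section 6.4, for the delay comparison and its time trend:

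- State the window close, and use cases registered within the same standard window for every incident year.
- Analyse delay as right-truncated, by reverse-time hazard regression or a likelihood conditional on delay not exceeding window close minus diagnosis date. Use this model for the type and age contrasts, the specialty-care and hospitalization question, and calendar time.
- State results as conditional on registration within the window.
- Report, by type, age and incident year, the share of cases found only outside the window, with the sweeps that each cohort received, so that late T2D cases remain visible.
- Keep registration as the endpoint.

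The diagnosis date, registration date and out-of-window flag are already part of the registry, so no new data collection is needed. The cost is a few lines of text, a different standard survival routine, somewhat wider intervals and a conditional interpretation.
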